
Adalimumab is a recombinant full-length human immunoglobulin (IgG1) monoclonal antibody containing only human peptide sequences. Adalimumab is produced by recombinant DNA technology in a mammalian cell expression system. Adalimumab is comprised of fully human heavy and light chain variable regions, which confer specificity to human TNF, and human IgG1 heavy chain and kappa light chain sequences. Adalimumab binds with high affinity and specificity to soluble TNF- α but not lymphotoxin (TNF- β). Adalimumab has been approved for therapeutic use in rheumatoid arthritis, ankylosing spondylitis and psoriatic arthritis.

In Crohn's disease Adalimumab was shown to be effective in 4 controlled clinical studies in subjects with moderate to severe active Crohn's disease, including more than 1400 patients. CLASSIC I was a 4 week trial that showed the effectiveness of Adalimumab in the induction of remission of CD in anti-TNF naïve moderate to severe Crohn's disease patients. The trial assessed three different Adalimumab dosing regimens, with prior efficacy of the dosing regimen of 160 mg at week 0 and 80 mg at week 2. GAIN demonstrated the effectiveness of Adalimumab at the 160 mg (week 0) and 80 mg (week 2) loading dose, for the induction of remission in Crohn's disease patients who had loss of response, or were intolerant to infliximab. CHARM was the pivotal efficacy and safety trial for the maintenance use of Adalimumab in Crohn's disease demonstrating the significant efficacy of Adalimumab compared with placebo in sustained remission over 1 year. The study population included both anti-TNF naïve and anti-TNF experienced patients. In CLASSIC II patients of CLASSIC I were continued and received either 40 mg every other week or 40 mg every week over 1 year. The trial demonstrated the effectiveness of both these regimens on sustained remission of Crohn's disease (12, 13).

4. Rationale

Hypothesis is that Adalimumab is well tolerated under every day's conditions during long-term application in patients with Crohn's disease.

Adalimumab has recently received marketing authorization in Germany for the treatment of severe active Crohn's disease in patients not responding to the adequate therapy with steroids and/or one conventional immunosuppressive drug. This PMOS is designed to collect long-term data on the safety and efficacy of Adalimumab in patients with moderate to severe Crohn's disease in everyday clinical usage, prescribed in accordance

with the terms of the marketing authorization. Data on the safety and efficacy of Adalimumab will be collected from initial dosing and up to 60 months of therapy.

Well-designed observational cohort studies including a very strict study protocol and monitoring, are indispensable to complement the knowledge gained from randomized controlled trials with important real-life data. The gain in experience was recently demonstrated in the German register RABBIT in rheumatoid arthritis patients. RABBITT provided information that the majority of patients with various comorbidities, concomitant medications, dosing schemes, and disease states, who would not fulfill the inclusion criteria of a major trial, benefit from biologic therapy (14).

5. Study Objective

The primary objective of the non-investigational study (PMOS) is to demonstrate long-term efficacy and safety of Adalimumab in patients with Crohn's disease under routine conditions and to evaluate the proportion of patients achieving remission and the time to remission induction.

Secondary objectives include: Improvement/resolution of signs and symptoms of the acute Crohn's disease (CDAI –100), rate of adverse events, and long-term improvement of patients QOL.

Further, the observation study protocol enables physicians to characterize patients that fulfill criteria for Adalimumab treatment thus ensuring the requirements of reimbursement.

6. Investigational Plan

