6.4 Study Duration

The observation period for each individual patient starts with the administration of the initial dose of Adalimumab and ends after 60 months.

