Crohn's related surgery (incl. bowel surgery & number of surgeries)

Concomitant diseases

Concomitant medication (Crohn's related)

Crohn's disease activity before treatment

CDAI

Current manifestation of Crohn's disease and extraintestinal manifestation (EIM)

Laboratory values (leukocyte and thrombocytes count, hematocrit, C-reactive protein, gamma-glutamyl transpeptidase)

Pre-medication (Crohn's related): 5-ASA/Suflasalazine, steroids, immunosuppressants, TNF-inhibitors (incl. duration of treatment, reason for discontinuation; for prior adalimumab treatment: additionally documentation of former maintenance dose and interval), other biologicals

Average number of moderately severe to severe bouts of active disease per year over the past 3 years

Examinations prior to initiation of adalimumab therapy

Tuberculosis diagnostics & result (only if adalimumab therapy recently started)

Imaging techniques for disease activity assessment (i.e. endoscopy, ultrasonography, MRI or CT scan)

Mucosal healing status

Status for chronic hepatitis B

Initiation of adalimumab therapy

Date of initiation

Dose & interval

Follow-up Data (months 3, 6, 9, 12, 18, 24, 30, 36, 42, 48, 54, 60)

Weight

Adalimumab treatment continued/abrogated (reason for abrogation)

Adverse events/SAE

Crohn's disease activity during treatment

CDAI

Current manifestation of Crohn's disease, Fistula and EIM (incl. comparison of current disease activity with previous visit)

Crohn's related surgery since last visit (incl. bowel surgery & number of surgeries)

Mucosal healing

Change of adalimumab treatment (incl. change in dose & interval; if discontinued: reason for discontinuation; restart)

Change of concomitant Crohn's-related medication (steroids, immunosuppressants, antibiotics)

Laboratory values (leukocyte and thrombocytes count, hematocrit, C-reactive protein, gamma-glutamyl transpeptidase)

Imaging techniques for disease activity assessment since last visit (i.e. endoscopy, ultrasonography, MRI or CT scan)

Patients Questionnaire (months 0, 3, 6, 12, 24, 30, 36, 42, 48, 54, 60)

S-IBDQ (standard questionnaire)

Crohn's related hosptalization (within previous 3 months; incl. number of hopitalizations, duration of hospitalization)

Crohn's related work productivity impairment (within previous 3 months)

Final Data (month 60)

Global assessement of efficacy and safety, change of current Crohn's related medication, and adverse events

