7.6 Pregnancy Reporting

In the event of pregnancy, the physician will notify the Abbott contact person identified in Section 7.5 within 24 hours of the physician becoming aware of the pregnancy

8 Ethics and Quality

The German Drug Law defines an observational study as a data collection on routine use of medication, prescribed in the usual manner in accordance with the terms of the marketing authorization. In accordance to the code of contact of the German pharmaceutical industry the PMOS study protocol as well as the patients information and consent form will has been forwarded to the ethics committee of the German principal coordinating investigator [name]. [name]/Mainz for approval. The investigator will document the patients written consent and authorization to use and/or disclose personal and/or health data in the patients chart.

All patient data entered in the patient's case report form will be forwarded - without naming the patient - for evaluation to Abbott GmbH & Co KG and the biometrician online or in paper version. Each case report form bears a pre-printed patient identity number, which replaces the patient's initials. The date of birth will be replaced by the

patient's age at the start of the study. Accordingly, the patient's identity will not be disclosed to Abbott GmbH & Co. KG.

The data collection forms inclusive adverse event and serious adverse drugs reaction forms will be checked during data entry for missing or inconsistent data. These data will be completed through the use of data queries, if possible.

9 Case Report Forms

See also **6.5 Study conduct** for details

Data will be collected online or in paper version. The study comprises 4 different questionnaires to collect baseline data, data on therapeutic efficacy and safety during therapy with HUMIRA®, a final report on efficacy and safety and a patient questionnaire (German S-IBDQ).

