Each study center receives either online permission to a database or binders with a set of sheets for data collection, depending on the technical equipment of the centre. The required data should be entered in to the data sheets using the physicians' documentation. Any observation of an adverse event in the time period up-to 60 months, beginning with the initiation of HUMIRA® therapy, must be documented on the "Adverse Event Form", labeled 'Bericht über unerwünschte Ereignisse' and checked for severity. If the event fulfills the serious criterion (Serious Adverse Event) the "Adverse drug reaction report" form, labeled 'Bericht über unerwünschte Arzneimittelwirkungen' must be completed in addition.

10 Data Analysis Plans

All statistical analysis procedures are described in detail in a statistical analysis plan. This plan will be established by the biometric before the database will be opened for the first interims analysis, and signed by the sponsor, the principle investigator and the biometric.

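### The protocol does not settle whether efficacy documentation continues after adalimumab is stopped: section 4, the follow-up heading and section 9 tie it to treatment, section 6.4 to 60 months from the first dose

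*Protocol*

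**What the plan says.** Three places tie efficacy documentation to treatment:

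- Section 4 (Rationale): "Data on the safety and efficacy of Adalimumab will be collected from initial dosing and up to 60 months of therapy".
- Section 6.5, follow-up data, heading of the efficacy block: "Crohn's disease activity during treatment".
- Section 9, describing one of the four questionnaires: "data on therapeutic efficacy and safety during therapy with HUMIRA".

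Three places run on the calendar from the start of therapy:

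- Section 6.4: "The observation period for each individual patient starts with the administration of the initial dose of Adalimumab and ends after 60 months".
- Section 6.5: follow-up forms from month 3 to month 60, and a separate block, "Patients Questionnaire (months 0, 3, 6, 12, 24, 30, 36, 42, 48, 54, 60"), which holds the S-IBDQ.
- Section 9, for adverse events: "Any observation of an adverse event in the time period up-to 60 months, beginning with the initiation of HUMIRA® therapy".

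The follow-up list also asks for "Adalimumab treatment continued/abrogated (reason for abrogation") and, under change of treatment, "if discontinued: reason for discontinuation; restart". Section 7.4 collects serious adverse events only until 30 days or five half-lives after the last dose, whichever is longer.

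On analysis, section 10.2 takes in every patient with documentation and plans no separate intention-to-treat or per-protocol set. Section 10.3 leaves missing values missing. Section 10.1 expects 20% to 30% annual drop-out from 2000 patients.

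**The concern.** The primary objective is long-term efficacy and safety. A month-60 remission proportion means one thing among patients still taking adalimumab and another among all patients who started it. Patients who stop for lack of effect are the ones whose inclusion would most plausibly change the figure.

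The protocol leaves that choice open at the point of data collection. A site guided by section 4 and the form heading could close a patient at the stop visit or leave the efficacy block empty. A site guided by section 6.4 would document the same patient to month 60. Sections 10.2 and 10.3 contain nothing that offsets the difference, so the site's practice would pass directly into the late denominators.

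Two analyses planned in section 10.4 are also exposed. Where documentation ends with treatment, duration of therapy as a factor for remission coincides with length of follow-up. The assessment of centre effects may then partly reflect documentation practice.

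**Working it through.** The protocol states that no sample size calculation was made, so there is no figure of its own to reproduce. The check is mainly one of text.

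**Step 1: which window applies to which data after a permanent stop?**

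| Data | Wording tied to treatment | Wording tied to calendar |
|---|---|---|
| CDAI, manifestations, surgery, mucosal healing | Section 4; 6.5 heading; section 9 | 6.4; 6.5 visit months |
| S-IBDQ | Section 4, only as a general window | 6.4; fixed months in 6.5 |
| Adverse events | Section 4, only as a general window; section 9 form description | Section 9, 60 months from initiation |
| Serious adverse events | 7.4, last dose plus a short period | Section 9, as adverse events |

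**Step 2: does anything reconcile the columns?** The restart item can be completed only if some documentation follows a stop, which favours section 6.4. It does not cover a patient who stops for good. No other sentence says whether the efficacy items continue for that patient.

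**Step 3: how many patients could the rule affect?** Inputs from sections 6.2 and 10.1: N = 2000, annual drop-out d = 20% to 30%. Assumptions not in the protocol: all drop-out is treatment stop, nobody restarts, and nobody is lost for another reason. Still on drug at month 60 = N × (1 − d)^5.

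- d = 20%: 2000 × 0.8^5 = 655, so 2000 − 655 = 1345 have stopped (67%).
- d = 25%: 2000 × 0.75^5 = 475, so 1525 have stopped (76%).
- d = 30%: 2000 × 0.7^5 = 336, so 1664 have stopped (83%).

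These are upper bounds. If drop-out in 10.1 means loss of month-60 data, then 655 to 336 is simply the number expected to have data, and the number governed by the rule is unknown.

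**Step 4: direction, for illustration only.** Let s = (1 − d)^5, with month-60 remission in all starters = s × p_on + (1 − s) × p_off. The remission rates are assumed and do not come from the protocol. Take p_on = 60%.

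| p_off | On-drug only | All starters, d = 20% | All starters, d = 30% |
|---|---|---|---|
| 20% | 60% | 33% | 27% |
| 40% | 60% | 47% | 43% |
| 60% | 60% | 60% | 60% |

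The two readings agree only if remission is as frequent off drug as on it.

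**The case against.** The best answer is that there is only one working rule. Section 4 is a rationale, and its wording sets a ceiling. The operative sections, 6.4 and 6.5, run to month 60. The follow-up heading may only be the counterpart of the baseline heading for activity before treatment, and surgery is recorded since the last visit. Nothing tells a site to close a patient at the stop. This makes section 6.4 the more likely intention. It does not account for section 9, which repeats the treatment wording for the form itself, and it still leaves a permanent stop unaddressed.

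A second answer is that section 10.3 leaves minimum documentation to the statistical analysis plan, which is not shown and may contain a rule. However, section 10 requires that plan only before the database is opened for the first interim analysis. By then sites may already have closed patients, and an analysis plan cannot recover visits that were never documented.

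Several stronger readings are tempting but lack support:

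- *That sites will differ.* The text shows only that they may.
- *That the S-IBDQ is tied to therapy.* Its block runs on fixed months without mention of treatment.
- *That departures go unrecorded altogether.* Section 6.5 exempts only missed visit intervals.
- *That centre effects would show documentation habits instead of outcomes.* At most they could be mixed.
- *That the month-60 denominator is 2000 under section 6.4.* This needs zero loss over five years, against 10.1's own expectation. Any blended denominator needs a share of sites on each reading, which the protocol does not give.

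**Conclusion.** The inconsistency is real and should be corrected. Efficacy documentation is tied to treatment in three places and to 60 months from the first dose in others, and no passage covers CDAI, manifestations and surgery after a permanent stop. If documentation ends with treatment at some or all sites, the late efficacy results will rest mainly on patients still taking the drug. Treatment failures would be selectively absent. Quality of life is touched only through the general window.

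The size cannot be derived from the protocol. The range of 1345 to 1664 of 2000 patients is a ceiling that rests on reading all of the 10.1 drop-out as treatment stops with no other loss. Section 10.1 speaks of patients with data at month 60, so loss of data is its more natural meaning. A reader might infer that most of the cohort's late data are already compromised, but the document does not support that. It shows an ambiguity that favours section 6.4 without settling it.

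**What to change.** Make section 6.4 the single rule for documentation:

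- **Section 4:** say that data are collected up to 60 months after the first dose, whether or not adalimumab is continued.
- **Section 6.5:** reword the follow-up heading to disease activity since the last visit. State that stopping adalimumab does not end documentation of CDAI, surgery and the patient questionnaire where these are assessed in routine care.
- **Section 9:** remove the restriction to therapy from the description of the follow-up questionnaire.
- **Forms:** record end of treatment and end of observation as separate items, each with date and reason.
- **Section 10.1:** say which of the two drop-out means.
- **Sections 7.4 and 9:** reconcile the serious adverse event window, tied to the last dose, with the adverse event window of 60 months from initiation.

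The cost is a wording amendment, a changed form heading and the separate end-of-observation item. Sites would also complete some extra routine-visit forms for patients no longer on adalimumab. Treatment itself is not affected.

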6.1 Selection of the Study Population

The study population will consist of patients with severe Crohn's disease.

Inclusion criteria: The inclusion criteria are as stated in the German Summary of Product Characteristics (SPC) 'Fachinformation' for $HUMIRA^{@}$

Exclusion criteria: The exclusion criteria are as stated in the German Summary of Product Characteristics (SPC) 'Fachinformation' for HUMIRA®

No additional inclusion and exclusion criteria are applicable since this project is non-interventional and Adalimumab will be used in a normal clinical setting according to the approved label.

Patients must provide the written informed consent to the investigator before entry into the PMOS.

6.2 Number of Patients to be Enrolled

The PMOS will include up to 2000 patients with active moderate to severe Crohn's disease.

6.3 Investigator Selection Criteria

The data for this observational study will be collected from IBD centers in Germany, and office based GI-specialists. Institutions, which have the capacity to enroll a minimum of five patients for Adalimumab in this observational study, will be included. Based on this, up to 400 sites will participate in the study.

6.4 Study Duration

The observation period for each individual patient starts with the administration of the initial dose of Adalimumab and ends after 60 months.

6.5 Study Conduct

This postmarketing observational study will be conducted in a single-arm, multi-center format.

6

Observational studies are intended to gather findings in the use of marketable medicinal products. Their special feature is that they do not influence, as far as this is possible, the physician in charge of the treatment in his diagnosis or choice and implementation of therapy for the individual case.

Adalimumab must not be prescribed for the purpose of including a patient in this observational study. Physicians are encouraged to treat their patients as in routine clinical practice. The patient is only identified for the study after the decision on the therapy had been made.

Patients who have active severe Crohn's disease and start treatment with Adalimumab in normal clinical settings according to label are documented. Adalimumab will be administered by sc injection. The dose regimen is recommended following the approved label: Either an initial dose of 160 mg adalimumab sc at Week 0 followed by 80 mg adalimumab sc at Week 2, or an initial dose of 80 mg adalimumab sc at Week 0 followed by 40 mg adalimumab sc at Week 2. Starting at Week 4 all subjects will receive 40 mg every other week (eow) sc in an open-label fashion. The PMOS documentation starts with the first application of Adalimumab, and is repeated at month 3, 6, 9, 12, 18, 24, 30, 36, 42, 48, 54, and 60.

The follow-up observation period is planned for five years and is focused on maintenance of efficacy and safety information during normal clinical settings. The physicians will follow up the patient via regular office visits at intervals as determined by routine clinical practice or as recommended by national guidelines. It is expected that follow up visits will be performed every three months during the first year and every six months during the subsequent four years. Baseline and follow up visits will be reported on different forms. Failure to observe these usual practice intervals of patient visits will not constitute a breach or violation of the protocol.

The following data will be documented (if assessed in routine care):

Baseline Demographic Data (month 0)

Age

Gender

Height

Weight

Smoking behavior

Informed Consent

Informed consent signed by patient

Medical History

History of Crohn's disease

- Date of first diagnosis
- First manifestation of Crohn's disease

Local of luminal disease

Fistula

Stenoses

Extra-intestinal manifestation

Crohn's related surgery (incl. bowel surgery & number of surgeries)

Concomitant diseases

Concomitant medication (Crohn's related)

Crohn's disease activity before treatment

CDAI

Current manifestation of Crohn's disease and extraintestinal manifestation (EIM)

Laboratory values (leukocyte and thrombocytes count, hematocrit, C-reactive protein, gamma-glutamyl transpeptidase)

Pre-medication (Crohn's related): 5-ASA/Suflasalazine, steroids, immunosuppressants, TNF-inhibitors (incl. duration of treatment, reason for discontinuation; for prior adalimumab treatment: additionally documentation of former maintenance dose and interval), other biologicals

Average number of moderately severe to severe bouts of active disease per year over the past 3 years

Examinations prior to initiation of adalimumab therapy

Tuberculosis diagnostics & result (only if adalimumab therapy recently started)

Imaging techniques for disease activity assessment (i.e. endoscopy, ultrasonography, MRI or CT scan)

Mucosal healing status

Status for chronic hepatitis B

Initiation of adalimumab therapy

Date of initiation

Dose & interval

Follow-up Data (months 3, 6, 9, 12, 18, 24, 30, 36, 42, 48, 54, 60)

Weight

Adalimumab treatment continued/abrogated (reason for abrogation)

Adverse events/SAE

Crohn's disease activity during treatment

CDAI

Current manifestation of Crohn's disease, Fistula and EIM (incl. comparison of current disease activity with previous visit)

Crohn's related surgery since last visit (incl. bowel surgery & number of surgeries)

Mucosal healing

Change of adalimumab treatment (incl. change in dose & interval; if discontinued: reason for discontinuation; restart)

Change of concomitant Crohn's-related medication (steroids, immunosuppressants, antibiotics)

Laboratory values (leukocyte and thrombocytes count, hematocrit, C-reactive protein, gamma-glutamyl transpeptidase)

Imaging techniques for disease activity assessment since last visit (i.e. endoscopy, ultrasonography, MRI or CT scan)

Patients Questionnaire (months 0, 3, 6, 12, 24, 30, 36, 42, 48, 54, 60)

S-IBDQ (standard questionnaire)

Crohn's related hosptalization (within previous 3 months; incl. number of hopitalizations, duration of hospitalization)

Crohn's related work productivity impairment (within previous 3 months)

Final Data (month 60)

Global assessement of efficacy and safety, change of current Crohn's related medication, and adverse events

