6.5.1 Description of Activities

For all study centers participating at the CARE Crohn's study (Phase IIIb) a follow-up in the PMOS is provided.

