10.2 Study population

The study population contains data of all documented patients. According to chapter 5 the objective of the study is the Adalimumab therapy in patients with Crohn's disease under routine conditions. Therefore a separate analysis for intention to treat population and per protocol population is not planned.

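### Observation is defined from the first adalimumab dose, yet the baseline form and the CARE follow-up indicate that previously treated patients also enter, and one study population holds them all

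*Protocol*

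**What the plan says.** **First dose as the start.** Protocol 6.4: "The observation period for each individual patient starts with the administration of the initial dose of Adalimumab and ends after 60 months". Section 4 (Rationale) gives the same data window. Section 6.5 describes the documented patients as those beginning adalimumab in routine care and starts documentation at the first administration.

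**Signs of earlier exposure.** The baseline list in 6.5 includes "Tuberculosis diagnostics & result (only if adalimumab therapy recently started". Its pre-medication item adds "for prior adalimumab treatment: additionally documentation of former maintenance dose and interval". Section 6.5.1 reads: "For all study centers participating at the CARE Crohn's study (Phase IIIb) a follow-up in the PMOS is provided".

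**One population.** Section 10.2: "The study population contains data of all documented patients". The same section plans no separate intention-to-treat and per-protocol analyses.

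**Where it is used.** The primary objective in Section 5 includes how many patients reach remission and how long induction takes. A 100-point fall in CDAI is a secondary objective. Section 10.4 adds logistic models for remission and Cox models for time to remission. Its subgroups are to be chosen from the regression results, not by prior exposure.

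**Severity, a side issue.** Section 6.1: "The study population will consist of patients with severe Crohn's disease". Section 6.2: "The PMOS will include up to 2000 patients with active moderate to severe Crohn's disease".

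**The concern.** A new-starter cohort and a cohort that includes established users need different time origins and support different endpoints. The text of 6.4 and 6.5 describes the first kind. The baseline form is written as if the second kind also occurs.

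If patients with an earlier first dose are analysed together with new starters, the remission part of the primary objective suffers most:

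- A patient who enters in remission has a zero or undefined time to induction.
- A CDAI recorded at entry under treatment cannot serve as the pre-treatment reference for a 100-point fall, unless a historical value is retrieved.
- Patients who reach PMOS entry while still on the drug have been selected for tolerating it and staying on it.

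**Working it through.** The plan gives no figure to reproduce: 10.1 says that the sample size was not calculated. The check compares sections and then illustrates the possible size.

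**1. Do the sections agree?** If every patient is documented from the first dose (6.4, 6.5), every patient has recently started. The condition on the tuberculosis item would then always be met and would have no purpose. It does work only if some patients enter after therapy is established. The prior-adalimumab item shows that patients with an earlier first dose are expected, though these may be restarters. The CARE sentence points the same way but names centres, not patients.

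**2. Which quantities are affected for a patient whose first dose came before entry?**

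- *CDAI before treatment (6.5 baseline).* Not a pre-treatment value for a continuing patient. It can be a valid pre-retreatment value for a restarter.
- *Time to remission induction (Sections 5 and 10.4).* The interval from first dose to entry is not observed.
- *Adverse events.* Section 9 documents events from initiation of therapy, but 7.4 collects serious events only from consent or authorization. Counting a continuing patient's person-time from first dose would add pre-consent time in which serious events were not collected, and so lower the early rate.

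**3. Shift in the pooled remission proportion.** Let p be remission in new starters, q in continuing patients and f the share of continuing patients. All three are assumptions.

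Pooled = (1 − f)·p + f·q, so shift = f·(q − p).

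With p = 0.40 and q = 0.70:

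- f = 0.10: 0.90 × 0.40 + 0.10 × 0.70 = 0.43, shift +3 points
- f = 0.20: 0.80 × 0.40 + 0.20 × 0.70 = 0.46, shift +6 points
- f = 0.40: 0.60 × 0.40 + 0.40 × 0.70 = 0.52, shift +12 points

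Over p = 30–50%, q = 50–90% and f = 10–50%, the shift runs from 0 (p = q = 50%) to 30 points (0.50 × (0.90 − 0.30)). This grid contains no case with q < p. Where q < p, the formula gives a negative shift.

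**4. Selection before entry.** Section 10.1 assumes an annual drop-out of 20% to 30%. If the same rate applied between first dose and entry (an assumption), the share of starters already lost is 1 − (1 − d)^t:

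- entry after 1 year: 20% (d = 0.20) to 30% (d = 0.30)
- entry after 2 years: 1 − 0.80² = 36% to 1 − 0.70² = 51%

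**The case against.** The strongest reply is that no eligibility rule admits continuing patients. The only direct description of who is documented, in 6.5, is of patients beginning the drug. A reader might infer that the protocol openly plans to pool continuing patients and CARE roll-over patients with new starters. The text does not go that far:

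- The prior-adalimumab item stands among pre-medications, next to the reason for discontinuation, and fits patients who stopped and are restarting.
- Section 6.5.1 does not say what CARE patients received or that they transfer.
- Section 10.2 mainly explains why intention-to-treat and per-protocol sets are not separated. It does not fix one denominator for every endpoint.
- Section 10.4 names duration of therapy as a possible factor for remission, and the SAP, not shown, may define endpoint-specific sets or delayed entry.
- A reader might also infer that pooling must overstate remission. That rests on assumed rates. Restarters after an earlier failure could remit less often, and the share of previously treated patients may be small.

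All of this stands, and it makes entry of continuing patients an inference and the direction of bias conditional. It does not explain the condition on the tuberculosis item, which is hard to reconcile with a cohort documented from the first dose. Nor can an SAP settle who may enter. Even restarters alone have a first dose before entry, so the start rule in 6.4 would not fit them.

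**Conclusion.** The point holds as an inconsistency within the protocol that reaches its primary objective. Sections 4, 6.4 and 6.5 set the start at the first dose, while the baseline items in 6.5, supported by 6.5.1, indicate that some patients had their first dose earlier. Section 10.2 sets no one apart. For continuing patients, induction, CDAI response and time to remission from first dose cannot be measured as intended.

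Pooling would probably raise remission and lower early event rates. The size cannot be derived from the document: +3 to +12 points is an illustration under 40% versus 70% remission and shares of 10% to 40%. The conclusion rests on reading the tuberculosis condition as purposeful. If the sponsor confirms that only first-time users enter, what remains is to correct the form items and clarify 6.5.1.

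The severity wording is a separate, minor matter. It has no bearing on the time origin.

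**What to change.** **Protocol 6.4 to 6.5.1.** State whether patients with ongoing or prior adalimumab, including any from CARE, may enter, and what month 0 means for them. Make the form items agree with that answer.

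**Section 10.2.** Define three sets from the date of initiation, the enrolment date, prior adalimumab and a CARE-origin flag:

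- (a) *New starters not in remission at baseline*: the only set for remission induction, 100-point CDAI response and time to remission. New starters already in remission are counted and kept for description and safety.
- (b) *Restarters after a documented stop*: reported separately, from their re-initiation date.
- (c) *Continuing or roll-over patients*: reported separately for maintenance and safety. Keep first dose as the time scale, with delayed entry at enrolment, so that no person-time before enrolment is counted. Resetting the clock to zero at enrolment is a different method and would mix early and late exposure.

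**Cost.** Wording and derived flags. Date of initiation and prior adalimumab are already on the form. The form must distinguish first start from restart, hold the enrolment date and, if needed, carry the CARE flag. The induction endpoints lose some denominator.

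**Minor.** Reconcile severe disease (6.1, 6.5) with moderate to severe disease (Section 4, 6.2), so that conclusions refer to one population.
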